2. STUDY OBJECTIVES

The aim of this clinical study is to determine whether the proposed treatment represents a valid and significant treatment for ulcers by evaluating the percentage reduction of the area of the wound over a 10-week observation period and comparing the reduction of the area of the wound (or part of the wound), both on the same patient and within the entire group, treated with the EmoLED device, versus the control wound (or part of the wound) treated with a standard method. Over the 10-week period following their recruitment, the patients will continue to take their usual topical therapy and attend the weekly visits. Patients will be monitored:

- until healing, if this occurs before week 10,
- until week 10 in the event of incomplete healing.

Additionally, given that the device does not yet have CE marking, reports and assessments on the safety and usability of the device will be complied by the medical staff during the study.

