For each new patient, the Principal Investigator or his/her delegate will complete the Patient Enrolment Form with information such as patient identification (Name and Surname will be the same as in the Case Report Form, i.e., site ID code and number), age, gender, root cause of the ulcer, any concomitant conditions, any pharmacological therapies, date of onset of ulcers and recruitment date.

The second part of the form contains a table for recording the visit date, the patients' general health and the data collected at each visit.

Recording of clinical data

The data pertaining to the evaluation of the study endpoints will be acquired at specific time points as indicated in the Protocol and in the Study Case Report Form.

The parameters recorded on the Case Report Form will be acquired and maintained in paper format for the entire duration of the trial and stored both in paper and digital format, after scanning the Case Report Form, once a patient has completed the study; photographic images of wounds will be acquired, maintained and stored in digital format for the entire duration of the trial and afterwards.

The archiving code follows the patient recruitment code and the time of acquisition.

Case Report Form

The same Case Report Form will be used for all patients. It consists of many columns to be completed, one for each observation time point. At each observation time point, the doctor will mark the value chosen for each parameter with an "X" and the most appropriate description.

The Case Report Form will include a "Notes" section for recording additional information not initially envisaged that may be useful during the data analysis phase (e.g., patient's ethnic origin, special environmental conditions, patient's specific health conditions such as influenza or others, etc.).

Following the patient's completion of or withdrawal from the study, the Case Report Form will be scanned and archived.

Centralised database

The Principal Investigator of each site will send the Enrolment Form of any new recruited patients as well as the photographic records of the follow-up patients to the Project Manager on a weekly basis. The Case Report Forms of all patients who leave the study, whether healed or identified as drop-outs, will also be submitted.

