If, at recruitment, a patient has more than one wound with a **diameter greater than 5 cm**, all wounds will be divided into two halves along the longest side and treated as described above.

After treatment with the EmoLED device, the wound will be dressed with a hydrofibre dressing. If clinical signs of infection occur, the wound will be dressed with a hydrofibre dressing with silver. The limb will then be bandaged with a compression bandage.

4.1.2 Standard treatment and data recording.

Any wounds or parts of wounds that are not treated with the EmoLED device will be medicated using the standard treatment consisting of a hydrofibre dressing or hydrofibre dressing with silver (as described above) and compression therapy. Ultimately, the treatment differs only for the fact that the EmoLED device is used in accordance with the procedure described above, while the rest of the treatment remains unchanged.

Following enrolment and the signing of the Informed Consent Form, the pertinent data from each patient will be recorded in the respective Case Report Form according to the following schedule: W0 (Week 0: enrolment and first treatment), W1, W2, W3 ... to W10, as per the routine visits over the 10-week period from enrolment.

Patients may miss a maximum of two non-consecutive follow-up visits over the 10-week period, starting from visit 5. Patients will be excluded from the study if consecutive visits are missed.

The parameters used to define the study outcomes will be based on:

- photographic images of the wounds treated with the EmoLED device as well as of control wounds
- Case Report Form completed by the doctor during the visits.

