6. STATISTICAL PLAN

Ninety subjects will be enrolled in this study. Each subject is part of both the control group and the treatment group.

Given that each patient will both receive the treatment and will also be a control subject, both groups will contain the same number of subjects, even if some of the subjects withdraw from the study. A comparative study of the subjects' demographic data and other baseline characteristics will also not be necessary as the two groups will be perfectly superimposable.

Treatment will be administered immediately after the cleaning and any necessary debridement of the complete wound. The area of the wound that should not be treated with the EmoLED device will be duly marked and covered with different layers of sterile dressing; this facilitates treatment standardisation and uniformity, thereby limiting any variability; it will also enable the treated, untreated and adjacent areas of each subject to be coherently defined.

The aim of the statistical analysis will be to establish the efficacy of the treatment with the EmoLED device; the significance ($p<0.05$) of any difference observed in the healing process between treated and untreated areas will be evaluated. Specifically, the primary endpoint of the study is the percentage reduction of the area of the wound treated with the EmoLED device versus the wound not treated with the EmoLED device at W10.

The secondary endpoints are:

1. Treatment safety.
2. Outcomes comparison in terms of the percentage reduction of the area of the wound treated with the EmoLED device versus the wound treated with SOC only within the ten-week observational period.
3. Evaluation of difference in healing time between the two areas.
4. Pain reduction (with pre-treatment assessment on a 0-10 VAS)
5. (OPTIONAL) Depending on the patient's willingness to continue to go to the study site, the observation of any unhealed area(s) over the 10-week period can be extended until complete healing or up to 20 weeks.

Estimation of sample size

The considerations underlying the choice of the model described below were drawn from a review of the literature on leg ulcer therapies and healing dynamics as well as on past clinical experience data obtained by the sites involved in the study with the treatment in question.

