The most significant finding yielded by the analysis of the clinical data in our possession is an expected 30% variability in the percentage reduction of the area of the wound at week 10. This value was confirmed by [15], where it was used to estimate the sample size. On the other hand, [16] found the standard deviation of the percentage reduction of the area of the wound to be 53% in the worst case and limited to venous ulcers only.

The analysis for the calculation of the sample size is based on:

- the clinical objective, which is represented by the percentage reduction of the area of the wound at W10
- a non-parametric statistical instrument for paired data, namely the Wilcoxon signed-rank test
- an a priori hypothesis of expected variability of 50% (conservative value)
- an expected 20% mean difference in the percentage reduction between the treated and the non-treated area
- a statistical power of 80% ($\beta=0.2$) and $\alpha=0.05$ will be considered
- a unilateral alternative hypothesis: the EmoLED treatment does not result in worsened outcome
- A correlation coefficient between percentage reductions of the treated and untreated area of 0.1, 0.3, 0.5 and 0.7
- A method for estimating the sample size based on asymptotic relative efficiency, compared to the t-test (minARE)

| | Estimate 1 | Estimate 2 | Estimate 3 | Estimate 4 |
|---|------------|------------|------------|------------|
| β | 0.2 | 0.2 | 0.2 | 0.2 |
| α | 0.05 | 0.05 | 0.05 | 0.05 |
| Diff. in % wound area reduction after 70 days | 20% | 20% | 20% | 20% |
| ρ | 0.1 | 0.3 | 0.5 | 0.7 |
| n | 83 | 65 | 47 | 29 |

The higher estimate is that relating to case 1, whose sample size is 83 subjects, which served as the basis for the choice of the number of subjects to be recruited, taking into account possible loss of subjects during treatment.

Statistical analysis of the primary endpoint.

A Wilcoxon signed-rank test with a significance level of 0.05 will be performed to evaluate the efficacy of use of the device. This test allows paired data to be handled and is robust enough to evaluate variability in observation distribution. A population analysis, as well as a per-protocol analysis (PP), will be performed for the subjects who complete the study.

Statistical analysis of secondary endpoints.

1. Treatment safety.

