Adverse event reports will be collected, analysed and managed according to the criteria indicated in 5.2. The most appropriate statistical instrument will be chosen for analysis based on the number and type of adverse events reported.

2. Outcomes comparison as percentage reduction of the area of the wound treated with the EmoLED device versus the wound treated with SOC alone during the 10-week observation period.

Both the areas of the wound treated with the EmoLED device and those not treated with the EmoLED device, as measured on the required observation days, will be considered. A statistical analysis of paired data will be

performed using repeated measurements. In particular, both a comparison of the measurements obtained on different days, separately, and an analysis that will take into account the global trend over the observation period, will be performed.

Tests for data paired to pairs of measurements obtained on different observation days will be performed in the first case. These tests will be applied separately to the various days, evaluating any significant differences in both treated and untreated areas. The adopted statistical test will be either a parametric (t-test) or a non-parametric test (Wilcoxon signed-rank test) depending on the observed data distribution. The statistical significance will be corrected for multiple comparisons (e.g., given the possibility of a positive correlation between the identified measurements, Benjamini-Hochberg correction will be considered).

In the second case, the area under the curve (AUC) will be evaluated for each subject and in each area in order to obtain information on possible differences between changes in the treated and untreated areas of the wound. Either parametric or non-parametric paired data tests (depending on parameter distribution) will be performed in order to evaluate any differences in the trends of this parameter summarising the healing dynamics both in the treated and untreated areas.

The mean value observed in the remaining subjects will be used for both approaches if there is any missing data. A sensitivity analysis will be performed using both the best value and the worst value observed in the subjects.

3. Evaluation of the difference in healing time between the two areas.

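### Secondary endpoint 2 fills missing values with the mean of the remaining subjects: a per-area fill makes paired p-values too small, and closed wounds have no stated score

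*Combined protocol and SAP*

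**What the plan says.** Section 6, secondary endpoint 2, plans two approaches: paired tests on separate observation days (t-test or signed-rank, with a Benjamini-Hochberg type correction) and a paired comparison of each subject's AUC in the two areas. The missing-data rule is: "The mean value observed in the remaining subjects will be used for both approaches if there is any missing data". A sensitivity analysis uses the best and the worst observed value instead. Optional endpoint 5, with follow-up of unhealed areas to week 20, is analysed in the same way.

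Other sections determine which values go missing:

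- Section 2: patients are monitored "until healing, if this occurs before week 10", otherwise to week 10.
- Section 3.3, Centralised database: "The Case Report Forms of all patients who leave the study, whether healed or identified as drop-outs" are to be submitted. Healed patients therefore leave, and they are told apart from drop-outs.
- Section 4.1.2: "Patients may miss a maximum of two non-consecutive follow-up visits over the 10-week period, starting from visit 5". It adds: "Patients will be excluded from the study if consecutive visits are missed".
- Section 6: "both groups will contain the same number of subjects, even if some of the subjects withdraw from the study". The calculated 83 subjects become 90 "taking into account possible loss of subjects during treatment". No drop-out rate is given.

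No section says whether the mean is per area, per visit or pooled, and none gives the value of an area after it has closed.

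**The concern.** Two separate problems follow from the one sentence.

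**Understated variance.** A patient who misses a visit is missing both areas. If each area is filled with its own mean at that visit, the filled difference equals the mean difference of the observed pairs. The pair adds to the count and nothing to the spread, so p-values come out too small. Benjamini-Hochberg takes those p-values as input and cannot repair them.

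**Closed wounds.** Follow-up stops because the wound has healed, so later values are absent by design for the patients with the best outcome. Read literally, the rule replaces a 100% reduction with the average of patients still attending. That under-reports healing in both areas. With per-area means it also gives pairs whose true difference is zero the difference of the unhealed pairs.

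Endpoint 2 is the trial's description of healing over the ten weeks, so its weekly p-values and mean curves are likely to be relied on.

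**Working it through.** **Inputs from section 6.** N = 90 pairs; SD 50 points per area; difference 20 points; correlation 0.1, 0.3, 0.5, 0.7; alpha 0.05; power 80%. The sample size uses "a unilateral alternative hypothesis: the EmoLED treatment does not result in worsened outcome", that is, one-sided. The analysis text gives no side, so both are shown.

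**The plan's own figure.** SD of the difference = 50 × sqrt[2(1 − rho)]. At rho = 0.1 this is 67.1, so the standardised effect is 20/67.1 = 0.298. With a one-sided noncentral t and effective sample size 0.864n (the minimum relative efficiency), n = 83, 65, 47 and 29, exactly as stated. The two-sided version gives 105, 82, 60 and 37. The margin for loss is 90 − 83 = 7, or 7.8% of 90.

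**Effect of a per-area fill.** Let m be the number of observed pairs. Filling the other N − m pairs leaves the mean difference and the sum of squares unchanged. The squared standard error falls from SS/[m(m − 1)] to SS/[N(N − 1)], so t is multiplied by

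f = sqrt[N(N − 1) / (m(m − 1))].

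One-sided size = P(T on m − 1 df > 1.662/f); two-sided size = 2 × P(T on m − 1 df > 1.987/f). The constants are the critical values on 89 df.

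| Filled pairs | m | f | Size one-sided | Size two-sided |
|---|---|---|---|---|
| 7 (the whole margin) | 83 | sqrt(8010/6806) = 1.085 | 0.065 | 0.071 |
| 18 (assumed 20%) | 72 | sqrt(8010/5112) = 1.252 | 0.094 | 0.117 |

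With 7 filled pairs, a one-sided p of 0.050 from the observed pairs is reported as 0.037.

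For the signed-rank test, null simulations (normal data, SD 50) give about 0.07 to 0.08 with 7 filled pairs. For the AUC only the visits after drop-out are filled, so the effect is somewhat smaller: roughly 0.06 to 0.07 with 7 drop-outs, assuming linear healing curves and drop-out at a random visit. Analysing observed pairs only keeps the size at 0.05.

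**Pooled mean.** Both areas receive the same value, so the filled difference is 0. The simulated size is about 0.05, with no inflation.

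**Closed wounds.** Assume 9 of 90 patients close both areas and leave. Their true difference is 0, so the true mean difference is (81/90) × d, where d is the mean among the 81 still attending. A per-area fill reports d, an overstatement of 90/81 = 1.11. For illustration, assume means of 53.8 (treated) and 37.1 (control) among the 81:

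- Treated: (81 × 53.8 + 9 × 100)/90 = 58.4, reported as 53.8.
- Control: (81 × 37.1 + 9 × 100)/90 = 43.4, reported as 37.1.
- Difference: 15.0, reported as 16.7.

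**The case against.** The strongest reply is that a closed wound has a known area of zero, so nothing is missing, and section 3.3 already separates healed patients from drop-outs. That reading is natural. If sites or the analyst follow it, the closed-wound problem does not arise. What stands is that the plan never says so, while its one explicit sentence covers any missing value.

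Second, few pairs may be filled. Section 4.1.2 excludes patients who miss consecutive visits and permits isolated misses only from visit 5, so misses within that rule cannot affect earlier weekly tests. This is fair. The 7-pair figure needs lost patients to be filled rather than excluded, which the plan leaves open; the 18-pair row is an assumption.

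Third, a best/worst sensitivity analysis is planned. It helps only in part, because it does not separate healed patients from drop-outs and it leaves the mean fill as the main analysis.

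Three stronger readings are tempting but not supported:

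- A reader might infer that a closed treated area is filled while its control is still measured, which would understate the effect during weeks 0 to 10. Section 4.1.1 has all wounds evaluated over the ten weeks, and section 2 ends monitoring by patient, so such a patient keeps attending. The situation is plausible only in the optional weeks 11 to 20.
- A reader might take the allowance of two missed visits as a count of missing pairs. It is a limit per patient and says nothing about how many pairs are missing at a visit.
- A reader might extend the problem to the primary result. The rule is written for endpoint 2 only, and section 6 ties the primary analysis to subjects who complete the study.

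**Conclusion.** The rule should be replaced. Under a per-area, per-visit mean it understates variance as a matter of arithmetic. With the only count the documents offer, 7 filled pairs, the nominal 0.05 becomes 0.065 one-sided or 0.071 two-sided for the t-test, provided those patients are filled and not excluded. Larger figures rest on assumed missingness, and a pooled mean removes the inflation. It would be too strong to say that every weekly p-value will be too small.

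Separately, the plan has no stated score for closed areas. Under the literal reading healing is under-reported. With per-area means the between-area difference is overstated as well, by a factor of 1.11 if an assumed 9 of 90 patients leave with both areas closed. Entering closed areas as zero removes this.

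The damage is confined to secondary endpoint 2 and optional endpoint 5. The primary and Akritas analyses do not use the rule.

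**What to change.** Replace the missing-data sentence and the sensitivity sentence after it with:

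> Once an area is recorded as closed, its reduction is set to 100% (area 0) at all later scheduled visits unless reopening is recorded. Other missing values are not filled with a mean. The weekly paired tests use the pairs observed at each visit. For the AUC, an isolated missed visit is interpolated between the adjacent visits; for a drop-out or a missed W10, both areas' AUCs are computed to the last visit at which both were measured and divided by the time covered. Best/worst-value fills are kept as a sensitivity analysis for all values that remain missing, but not for closed areas.

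State the same closed = 100% rule for the W10 value of the primary endpoint, so that the two analyses score a healed wound alike.

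The cost is SAP wording and a little programming, with no new data or visits and no change to the 83 or the 90. The drawbacks are slightly larger p-values than the mean fill would show, AUCs over unequal follow-up for drop-outs, and no way to see a wound reopen after the patient has left.

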4.3 Secondary endpoints

The following secondary endpoints were identified for this study:

1. Treatment safety.
2. Outcomes comparison in terms of the percentage reduction of the area of the wound treated with the EmoLED device versus the wound treated with SOC only within the ten-week observational period.
3. Evaluation of difference in healing time between the two areas.
4. Pain reduction (with pre-treatment assessment on a 0-10 VAS)
5. Depending on the patient's willingness to continue to go to the study site, the observation of any unhealed area(s) over the 10-week period can be extended until complete healing or up to 20 weeks.

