A survival analysis will be performed based on the Akritas test applied to the Kaplan-Meier curve. This type of analysis is used to evaluate the time from observation to the event of interest (time-to-event). In particular, in this case, the event will be a percentage reduction of the area of the wound of $\geq 70\%$ at W10. This approach will allow both paired data and the possibility that some of the subjects may be non-adherent to the protocol and withdraw from the study to be managed. A curve will be constructed for each group, each corresponding to the analysis of the two areas, both that treated with the EmoLED device and that not treated with the EmoLED device. The Akritas test is based on a transformation into ranked "survival" times, understood as time to event of interest (time-to-event). In particular, in this case, the event will be a percentage reduction of the area of the wound of at least 70% at W10. Ranked observations will be transformed according to a model that takes into account the possibility that they may be truncated or censored.

4. Pain reduction (pre-treatment assessment on a 0-10 VAS).

A non-parametric analysis will be performed using the Friedman test, which can be considered the non-parametric equivalent of the ANOVA test for repeated measurements.

5. (OPTIONAL) Depending on the patient's willingness to continue to go to the study site, the observation of any unhealed area(s) over the 10-week period can be extended until complete healing or up to 20 weeks.

The analysis will be performed as for endpoint 2.

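### Secondary endpoint 3 is called healing time, but its event is a 70% area reduction fixed at W10, with no rule for when the event occurs

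*Combined protocol and SAP*

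**What the plan says.** Section 4.3, item 3, names the endpoint: "Evaluation of difference in healing time between the two areas". Section 6 uses the same name in its list of endpoints and again as the title of the analysis: "Evaluation of the difference in healing time between the two areas".

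Under that title, section 6 plans one Kaplan-Meier curve for the treated areas and one for the control areas. They are compared with the Akritas test for paired data, which works on ranked times and allows for censoring. The event is defined twice in nearly the same words: "in this case, the event will be a percentage reduction of the area of the wound of at least 70% at W10". Time is described only as running from observation to the event. No starting visit, first-visit rule or censoring date is given.

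Elsewhere healing is an end state. Section 2 monitors patients "until healing, if this occurs before week 10" and otherwise "until week 10 in the event of incomplete healing". Section 3.3 refers to "The Case Report Forms of all patients who leave the study, whether healed or identified as drop-outs", so being healed is a way of leaving the study. Section 4.3, item 5, says that observation of areas not yet healed "can be extended until complete healing or up to 20 weeks". The opening of section 6, by contrast, uses the word for a gradual process: "any difference observed in the healing process between treated and untreated areas will be evaluated".

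The other efficacy analyses of wound area are the percentage reduction at W10 (primary), paired tests by visit day plus an area under the curve (endpoint 2), and the same methods again for the optional extension (endpoint 5).

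**The concern.** The introduction gives a shorter healing time as the potential benefit of the device, and endpoint 3 is the only analysis that carries that name. Three things do not fit together.

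- The name promises a time to healing, but the event is a partial reduction in area.
- The event is tied to a single visit, but the method needs an event time for each area.
- Time to complete closure is not analysed anywhere, so no other result could support a statement about healing time.

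At stake is what the trial may conclude from this endpoint. A favourable result could be reported as faster healing for areas that are still open. Two analysts working from the same records could also derive different event times.

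A related uncertainty concerns follow-up. Section 2 stops monitoring at healing, at patient level, but every patient contributes at least two areas. The text does not say whether one closed area is enough to stop.

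**Working it through.** **1. The plan's own figures.** Endpoint 3 has no stated event count, power or sample size. The sample-size table in section 6 is for the primary endpoint. Its inputs are a standard deviation of 50 points, a difference of 20 points, one-sided alpha 0.05, power 80%, and correlations of 0.1, 0.3, 0.5 and 0.7. The standard deviation of the paired difference is 50 × √(2(1 − ρ)); for ρ = 0.1 this is 50 × √1.8 = 67.1. A noncentral t calculation with effective size 0.864 n gives 83, 65, 47 and 29, exactly as printed. The factor 0.864 is the standard value for the minARE method and is an assumption here, because the plan does not print it. No input comes from endpoint 3, so correcting endpoint 3 does not change the sample size.

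**2. The event read literally.** Let R(w) be the percentage reduction at week w. The event is R(10) ≥ 70.

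- Every event has time 10, so there is one distinct event time.
- The Kaplan-Meier curve is 1 before week 10 and has a single step there, to 1 − d/n, where d is the number of areas with R(10) ≥ 70 and n the number still under observation at W10.
- All event times are tied, so the comparison reduces to a paired yes/no comparison at W10.
- An area that first reached 70% at W3 and one that first reached it at W10 receive the same time, if both still meet the criterion at W10.
- A patient whose areas closed before W10 may have left the study and have no W10 measurement. The plan does not say how such areas count.

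This contradicts the ranked-time and censoring method in the same paragraph.

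**3. The event read as by W10.** Event time is the first attended visit w, from 1 to 10, with R(w) ≥ 70. The method then works, but the event is still not closure. The open share at the threshold is 1 − 0.70 = 0.30 of the W0 area.

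**4. The same area under two sections.** Take an area at 75% reduction at W10, with 1 − 0.75 = 25% still open.

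- Section 6, endpoint 3: it has had its healing-time event.
- Section 2: it is a case of incomplete healing at week 10.
- Section 4.3, item 5: it is unhealed and may be observed further, up to 20 weeks.

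**5. Time from 70% reduction to closure.** The documents give no healing curve and no definition of closure, so this gap cannot be derived, and no figure is offered.

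**6. Follow-up of the two areas.** Section 2 ends monitoring at healing of the patient. Section 4.1.1 says, for patients whose several wounds are all under 5 cm, that every wound is followed for the ten weeks. It does not repeat this for divided wounds. Endpoint 5 is worded by area. The sections are compatible if healing in section 2 means that all study areas have healed, but this is not written.

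**The case against.** The best case for the plan is that the event is declared in advance, twice, so a reader knows what healing time means here. Section 6 itself uses healing for a gradual process. A 70% threshold can be a legitimate surrogate, and it suits a trial whose stated aim is percentage area reduction over ten weeks. The W10 phrase is evidently a slip, since the same paragraph describes time-to-event data and censoring. W0, defined in section 4.1.2 as enrolment and first treatment, is the obvious time zero.

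Much of this stands. The threshold is not the defect, and by W10 is the likely intention. Nothing commits the trial to a closure endpoint, so a closure analysis is a useful addition and not a missing obligation. What does not stand is the name. A healing time needs an end point, and where the protocol uses healing as an end point it means complete healing. The first-visit rule and censoring date are also still unwritten.

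Two stronger readings are tempting. A reader might infer from section 2 that measurement of the second area stops once the first has closed, so that its censoring depends on its partner. The documents do not show this: section 4.1.1 and the per-area wording of endpoint 5 point the other way. A reader might also infer that the primary result is compromised. That would follow only if measurement did stop at the first closure, because the paired comparison at W10 would then lack a value for the other area.

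**Conclusion.** The point holds for the label and the event time. As written, the event definition contradicts its own method and, followed literally, removes the time comparison. On the probable reading, the analysis measures time to a 70% reduction, with up to 30% of the W0 area still open at the event. By itself it cannot support a statement that healing time is shorter.

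This rests on the plan's wording and on 1 − 0.70 = 0.30; no assumption about wound shape or healing curve is needed. The label and event-time problem concerns one secondary endpoint and leaves the sample size unchanged. The follow-up of the partner area is an ambiguity to be settled, not a shown error. It should be settled because, on the unfavourable reading, the primary comparison would be affected too. The correction should be made before the data are analysed.

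**What to change.** **(a) Event and time rule.** Delete the W10 phrase in both places. Call the analysis time to first area reduction of at least 70%. Take time as weeks from W0 to the first attended visit, up to W10, that meets the criterion. Count an area closed before W10 as an event no later than the visit at which closure is recorded. Censor areas without the event at their last measured visit, up to W10. This keeps the sponsor's event.

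**(b) Supportive closure analysis.** From the same weekly records and with the same paired method, report time to complete closure per area. Define closure in the SAP, including what it means for a half-wound bounded by the marker line. Reserve the term healing time for this analysis.

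**(c) Follow-up.** Reconcile section 2 with section 4.1.1 by stating, for divided wounds as well, that both areas are measured until both have closed or W10.

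The cost is a few sentences in the SAP and one in the follow-up rule; weekly records from W0 to W10 are already planned. The drawback of (b) is that fewer areas will close than will reach 70% by W10, so its power is lower. It should therefore be added as supportive and should not replace the 70% analysis.
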